5.9.4 PROVIDING L1-79 SUBSEQUENT TO THIS STUDY

If, in the opinion of the sponsor and the Investigator that L1-79 therapy is well tolerated and provides a beneficial therapeutic effect, an amendment to this study will be considered to provide L1-79 in an open label manner for subjects in this study who have either received placebo or who would likely benefit by receiving additional treatment at the end of the study.

Depending upon the results obtained during this investigation, if warranted, the sponsor may extend this study if the FDA permits. In the event that L1-79 therapy is found appropriate, the sponsor may adjust the dosing consistent with the findings of this trial and continue treating subjects beyond the specified treatment duration herein in a manner compliant with the FDA guidelines.

5.10 Discontinuation of Study Subjects

A patient may be discontinued for the following reasons:

- Non-compliance with treatment regimen or follow up requirements
- Lost to follow-up
- Patient and/or care giver requests voluntary withdrawal
- Adverse event sufficient in the opinion of the Investigator to warrant cessation of treatment
- Adverse event requiring unblinding of the patient's assigned treatment
- Investigator decision

Discontinuation for any reason will be documented in the eCRF and supporting documentation will be added to the patient file. Appropriate treatment will be provided for any disease or syndrome.

All subjects who receive a single dose, irrespective of discontinuation, will be followed for a period of 4 weeks subsequent to the first dose in order to determine whether the treatment was safe.

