- **Major Inclusion Criteria:** Males between 13 and 21 years of age, signed informed consent, normal clinical laboratory values, DSM-5 compliant diagnosis of autism spectrum disorder, confirmed by the Autistic Diagnosis Interview Review (ADIR), and by the Autism Diagnosis Observation Schedule (ADOS) score consistent with a diagnosis of autism, no more than one concomitant medication, on a stable regimen for at least 2 weeks prior to enrollment and no planned changes in psychosocial interventions during the trial.

- **Major Exclusion Criteria:** Any co-morbidities, including Fragile-X syndrome, epilepsy, Retts syndrome, ADHD, or other disease or syndrome aside from autism that requires treatment. Any other psychiatric disorder, or out of range lab values. DSM-5 diagnosis of schizophrenia, schizoaffective disorder, alcohol use disorder; active medical problems: unstable seizures (>2 in past month), significant physical illness.
- **Experimental Treatment:** L1-79 at doses of 100, or 200 mg, or placebo 3 times daily for 4 weeks.
- **Non-Experimental Treatment:** Placebo.
- **Dosage and Administration:** L1-79 or placebo, as assigned or as randomized, will be administered orally according to the regimen above.
- **Evaluation Schedule:** Subjects will be evaluated within one week prior to study accession, and weekly throughout the dosing period, and again 4 weeks after the cessation of treatment. The Assigned Dosage Groups (Groups 1 and 3) will have PK blood draws and EKG the randomized group will not have.
- **Safety Measures:** All Groups will have regularly scheduled complete history and physical examination that includes orthostatic blood pressure measurements, vital signs, CBC, differential, platelet counts, urine analysis, serum analytes including: total protein, albumin, glucose, BUN, creatinine, direct and total bilirubin, alkaline phosphatase, phosphorous, calcium, AST, ALT, sodium, potassium, chloride, bicarbonate, T₄, TSH, and adverse events assessments. The Assigned Groups (1 and 3) will also have electrocardiograms taken at the study screening visit and at the week 1.
- **Total Study Duration:** It is expected that the entire study from screening of the first patient until the last patient enrolled has completed the last visit to require a total of 36 weeks. This period was estimated to include an 8 weeks recruitment, 8 weeks for screening, and 8 weeks' for treatment of all patients enrolled in the study and 8 weeks for follow-up.

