3.2 Study Endpoints

3.2.1 SAFETY ENDPOINTS

Safety is the primary endpoint and analysis will focus on the following endpoints at each time point from the start of dosing through the 4-week treatment and observation period, and at a 4-week follow-up visit:

- EKG
 - Patients in the Assigned Dosage Groups (1 and 3) will also have an EKG at baseline and within 3 days prior to the their visits as described in [5.1.2](#).
 - In the event any EKG abnormalities appear to result from treatment in the Assigned Dosage Group then additional EKG may be required as described in section [5.5.2](#)
- Before and after the Active Treatment phase
 - Physical exam with vital signs, including orthostatic blood pressure
 - Hematology
 - Serum Chemistry
 - Urinalysis
- Active Visits, weeks 1-4
 - Vital signs findings, including orthostatic blood pressure,
 - Adverse Event (AE) reporting
 - Assessment of concomitant medications

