5.2 Drug Administration

5.2.1 THE L1-79 REGIMEN

Subjects will receive either 100 mg or 200 mg or matching placebo t.i.d. for a total of 28 days of dosing. The doses of L1-79 were determined based upon preliminary clinical research in subjects between 2½ and 24 years of age and doses between 90 and 200 mg t.i.d..

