5.9.2.8 Week 8 Follow-Up Visit (Study Day 56)

All patients are to receive:

- Physical exam with vital signs
- Hematology
- Urinalysis
- Serum chemistry
- Blood draw for storage
- ASD assessments will be performed, including: ABC, SRS, RBS-R, CGI-S SAS, VAB II, and CGI-I
- Record all adverse events
- Physical exam with vital signs
 - Question caregiver or patient about the patient's week, including questions regarding any changes in home life activities, events at school, sleep, or other matters germane to an understanding of the patient's autistic
 - Record concomitant medications

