5.13 Study Discontinuation Criteria

The occurrence of a grade 3 or 4 AE in any patient will result in the immediate discontinuation from this study. In the event of a grade 2 AE, the Investigator, at their discretion, may withhold treatment until the event resolves to grade 1 or less.

The Sponsor may at its discretion terminate the study as a whole if conditions warrant this action. The study site Investigator bears responsibility for orderly discontinuation of the study subjects enrolled at his/her study site.

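### The protocol gives conflicting lengths of safety follow-up for patients who stop early: 4 weeks from the first dose in section 5.10, 4 weeks after treatment or Day 56 elsewhere

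*Combined protocol and SAP*

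**What the plan says.** The statements on follow-up are these.

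- Section 5.10: "All subjects who receive a single dose, irrespective of discontinuation, will be followed for a period of 4 weeks subsequent to the first dose". The sentence gives judging safety as its purpose. It is the only follow-up duration in the discontinuation section.
- Section 5.2.1: treatment is given "for a total of 28 days of dosing".
- Synopsis, Evaluation Schedule: patients are seen before entry, weekly during dosing, "again 4 weeks after the cessation of treatment".
- Section 3.2.1: the primary safety endpoints are assessed "from the start of dosing through the 4-week treatment and observation period, and at a 4-week follow-up visit".
- Section 5.9.2.8, headed Study Day 56: "All patients are to receive" a physical examination with vital signs, hematology, urinalysis, serum chemistry and adverse event recording, among other items. Appendix A gives the same visit as Day 56 ± 2. Neither exempts patients who stopped early.
- Section 6.1.4: safety tables are to cover 8 weeks of treatment and 26 weeks of follow-up.

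On who leaves, section 5.10 lists adverse events among several reasons for discontinuation. Section 5.13 adds: "The occurrence of a grade 3 or 4 AE in any patient will result in the immediate discontinuation from this study". Section 5.14 terminates a patient whose grade 1 or 2 event recurs, or for whom the investigator judges continuing unsafe.

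**The concern.** The rules use different starting points. For a patient who takes all 28 days of drug, the synopsis and the Day 56 visit agree. For a patient who stops early, 5.10 gives Day 28, the synopsis gives 4 weeks after the actual last dose, and 5.9.2.8 gives Day 56.

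This bears on the primary objective because leaving treatment is partly driven by toxicity. Under 5.13 a grade 3 or 4 event takes the patient out of the study, not merely off the drug. For such a patient a site would naturally look to 5.10, and Appendix A has no early-termination visit to fall back on. A site that released the patient at Day 28 could say that it had followed the protocol.

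The causality scale is also affected. Sections 5.11.4 and 5.11.5 use improvement after stopping the drug as evidence for a probable or definite relationship, and that needs off-drug observation. With 40 patients in total, a few short records would be visible in descriptive adverse event tables.

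**Working it through.** **Inputs.** Dosing lasts 28 days (5.2.1). The follow-up interval is 4 weeks (synopsis, 3.2.1). The follow-up visit is on Day 56 ± 2 (5.9.2.8, Appendix A). The 5.10 rule is 4 weeks from the first dose, taken as Day 0.

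**1. The plan's own figure.** 28 + 4 × 7 = 56. This reproduces the Day 56 visit exactly.

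**2. Total observation if 5.10 governs.** Follow-up ends on Day 0 + 28 = 28. The ratio to a completer is 28/56 = 0.50, or 28/58 = 0.48 to 28/54 = 0.52 across the ± 2-day window. It does not depend on the stopping day.

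**3. Off-drug observation if 5.10 governs.** For a last dose on Day d this is 28 − d days, against 56 − 28 = 28 for a completer seen at Day 56. The last column shows where 4 weeks after the last dose would fall.

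| Stop on Day d | Off-drug days, 28 − d | Share of 28 | Last dose + 28 |
|---|---|---|---|
| 1 | 27 | 0.96 | Day 29 |
| 7 | 21 | 0.75 | Day 35 |
| 14 | 14 | 0.50 | Day 42 |
| 21 | 7 | 0.25 | Day 49 |
| 27 | 1 | 0.04 | Day 55 |

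The off-drug shortfall is therefore small for early stops and nearly complete for late ones. The synopsis anchor adds d days to the 5.10 rule; the Day 56 visit adds 28 days whatever the stopping day.

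**4. Assessments at risk in the randomized groups (10 + 10 + 10 = 30 patients).** Appendix A and 5.5.1.2 schedule their physical examination at screening and at the 4-week follow-up. Section 5.7.1 also mentions one at visit 4, but 5.9.2.6 and Appendix A do not list it. Safety laboratory tests are at screening, Week 4 and the 4-week follow-up (5.5.1.8), and these groups have no 1-week post-dosing visit (5.1.3). Release at Day 28 loses the follow-up examination and the only laboratory tests scheduled after dosing. An early stopper who still attended Week 4 would have that draw off drug, but no section says whether the visit is kept.

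**5. The third window.** Section 6.1.4 implies (8 + 26) × 7 = 238 days, with twice the planned dosing period. It matches neither 28 nor 56 days, so the statistical section cannot settle the conflict.

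**6. Illustration only.** Assume a constant event hazard, which the documents do not give. If a share p of patients would have a first event by Day 56, the share by Day 28 is 1 − (1 − p)^(28/56). For p = 10% this is 5.1% (51% captured); for p = 40% it is 22.5% (56% captured). A lower hazard off drug would make the loss smaller.

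**The case against.** A reader might infer that the protocol deliberately follows early stoppers for only half as long as completers, and so biases the safety result toward L1-79. The documents do not support that.

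- Section 5.10 does not say that follow-up stops there. Its sentence covers every dosed patient, completers included. Read as a cap, it would also release completers at Day 28, against the visit schedule. It can be read as a minimum.
- Section 5.9.2.8 applies to all patients without exemption, and the synopsis anchor fits an early stopper.
- Half is correct for total time from first dose. It does not describe off-drug time, which runs from 27 days down to 1.
- Recovery is partly documented already. Section 5.11 records resolution time and outcome for each event, 5.11.6 requires monitoring of serious and life-threatening events until they disappear or are explained, and 5.14 ties resumption after a grade 1 or 2 event to its resolution.
- An event that causes a stop is itself recorded, and even under 5.10 every group is observed to Day 28. Some stops have non-safety causes. The documents give no discontinuation rate and no rate of events after stopping.

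All of this stands, and it limits the size of the point. It does not remove the conflict. The minimum reading is not written into 5.10, and under it a site that stops at Day 28 has still complied with that section. Section 5.11.6 follows events already identified; it does not look for new ones or schedule repeat tests. That the analysis is descriptive (6.1) does not help, since unequal windows affect counts as well as tests.

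**Conclusion.** The protocol contradicts itself on how long patients who stop early are observed for the primary safety endpoint, and nothing states which rule prevails. That conclusion rests on the text alone.

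The size is conditional on a site applying 5.10 as written: 28 days of total observation instead of 56, and 28 − d off-drug days instead of 28. The practical exposure is mainly late-onset non-serious events, laboratory changes and documentation of recovery. A bias toward a favourable safety result would further require toxicity-related stops to be more common on L1-79 than on placebo, which the documents neither state nor allow to be estimated. If sites follow 5.9.2.8 for everyone, the shortfall does not arise, but the documents do not ensure that.

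**What to change.** Choose one anchor for final safety follow-up and use it in the synopsis, 3.2.1, 5.9.2.8, 5.10, 6.1.4 and Appendix A. The sponsor should make the choice explicitly, because the candidates differ for early stoppers: for a stop on Day 7, 4 weeks after the last dose is Day 35, while the scheduled visit is Day 56. Offering both would keep the ambiguity.

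Reword the sentence in 5.10 so that it no longer ends follow-up 4 weeks from the first dose. It should say that every dosed patient, including one discontinued under 5.10, 5.13 or 5.14, has the follow-up safety assessments already listed in 5.9.2.8 at the chosen time, except after withdrawal of consent or loss to follow-up. State also whether the remaining weekly visits are kept. Correct the window in 6.1.4 to match, and report time under observation by treatment group beside the adverse event tables, so that any remaining imbalance can be seen.

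The cost is an edit to a few sentences and one already scheduled visit for the patients who discontinue. Some will decline it, and those cases should be counted.

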5.11 Recording of Adverse Events

Each patient will be observed and queried in a nonspecific fashion by the Investigator or designee at each visit during the study for any new or continuing AE that occurs since the previous visit. Any AE reported by the patient or noted by the Investigator or designee will be recorded in the Adverse Event section of the database. The following information will be recorded for each reported AE: description of the event, time of onset, time of resolution, severity, relationship to the study drug determined (as opposed to NSAID or antibiotic related toxicity), outcome, management of the AE, and outcome. Each AE will be classified as serious or not. Serious AE will be handled according to section [5.11.6](#).

Adverse events will be treated as deemed appropriate by the Investigator and the results will be recorded in the case report form, including any therapeutic regimens prescribed, hospitalization, surgery, discontinuation from the study or any other action related to the adverse event.

The Investigator should use the following definitions to classify the relationship of each adverse experience to the test treatment.

5.11.1 NOT RELATED

This category applies to those adverse experiences that, after careful consideration, the Investigators determines are clearly and incontrovertibly due to extraneous causes (disease, environment, etc.).

5.11.2 UNLIKELY: (MUST HAVE AT LEAST TWO OUT OF FOUR CRITERIA)

In general, this category can be considered applicable to those adverse experiences that, after careful medical consideration at the time they are evaluated, are judged to be unrelated to the study drug. An adverse experience may be considered unlikely to be related if or when:

- The adverse experience does not follow a reasonable temporal sequence* from administration of L1-79 or placebo.
- The adverse experience could readily have been produced by the patient's clinical state, environmental or toxic factors, or other modes of therapy administered to the patient.
- The adverse experience does not follow a known response pattern to the suspected drug.
- The adverse experience does not reappear or worsen when the drug is re-administered.

*Temporal sequence is defined as an association between the suspect drug and the observed reaction or event in which the suspect drug was present prior to the reaction or event as defined by history or drug blood level.

5.11.3 POSSIBLE: (MUST HAVE AT LEAST TWO OUT OF THREE CRITERIA)

This category applies to those adverse experiences for which, after careful medical consideration at the time they are evaluated, a connection with the study drug administration appears unlikely but cannot be ruled out with certainty. An adverse experience may be considered possibly related if or when:

- The adverse experience follows a reasonable temporal sequence from the time of immunization.
- The adverse experience follows a known response pattern to the study drug.
- The adverse experience could have been produced by other factors such as the patient's clinical state, therapeutic interventions, or concomitant drugs administered to the patient.

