5.11.4 PROBABLE: (MUST HAVE THREE OUT OF FOUR CRITERIA)

This category applies to those adverse experiences which, after careful medical consideration at the time they are evaluated, are felt with a high degree of certainty to be related to the study drug. An adverse experience may be considered likely related if or when:

- The adverse experience follows a reasonable temporal sequence from the time of drug administration.
- The adverse experience follows a known response pattern to the study drug.
- The adverse experience cannot be reasonably explained by other factors such as the patient's clinical state, therapeutic interventions, or concomitant drugs administered to the patient.
- The adverse experience is confirmed by improvement of the symptoms on de-challenge (e.g., the removal withdrawal, or discontinuation of the suspected drug from the patient's therapeutic regimen).

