5.11.5 DEFINITE: (MUST HAVE ALL FOUR CRITERIA)

This category applies to those adverse experiences that the Investigator feels are incontrovertibly related to the study drug. An adverse experience may be assigned an attribution of definitely related if or when:

- The adverse experience follows a reasonable temporal sequence from the time of drug administration.
- The adverse experience cannot be reasonably explained by the known characteristics of the patient's state, environmental or toxic factors, or other modes of therapy administered to the patient.
- The adverse experience occurs immediately following study drug administration, or improves on stopping the drug (de-challenge), or reappears on repeat exposure (re-challenge) (Note: this is not to be construed as requiring re-exposure of the patient, however, a category of definitely related can only be used when recurrence is observed).
- The adverse experience follows a known response pattern to the study drug.

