6.1.4 SAFETY

Adverse events will be coded using MedDRA and will be presented by body system and preferred term. Concomitant medications will be coded using [concomitant medication coding dictionary] and summarized by drug class and generic name.

Tables and graphs will show changes from baseline through 8 weeks of treatment and 26 weeks of follow-up in:

- Physical examination

- Vital signs
- Safety labs, including hematology and serum chemistry
- Cardiovascular changes, including orthostatic blood pressure.
- EKG changes from in the Assigned Dosage Group patients

Other safety data that will be presented include:

- Dose limiting toxicity
- Adverse events along with their severity and potential relationship to study treatment.
- Concomitant medications

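### The adverse-event causality criteria in 5.11.2 to 5.11.5 are neither exclusive nor exhaustive, with no precedence or default rule, so raters who follow the text can fill the relationship table differently

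*Combined protocol and SAP*

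**What the plan says.** Section 5.11 directs the investigator to classify the relationship of each adverse event using the definitions that follow. Not Related (5.11.1) rests on judgement alone. The other four categories count criteria:

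- **Unlikely (5.11.2)**: "UNLIKELY: (MUST HAVE AT LEAST TWO OUT OF FOUR CRITERIA". The criteria are no reasonable timing; another ready cause ("The adverse experience could readily have been produced by the patient's clinical state, environmental or toxic factors, or other modes of therapy administered to the" …); no known pattern ("The adverse experience does not follow a known response pattern to the suspected drug"); and a negative re-challenge ("The adverse experience does not reappear or worsen when the drug is re-administered").
- **Possible (5.11.3)**: at least two of three, namely timing, known pattern, and another possible cause. The timing criterion reads: "The adverse experience follows a reasonable temporal sequence from the time of immunization".
- **Probable (5.11.4)**: "PROBABLE: (MUST HAVE THREE OUT OF FOUR CRITERIA". The criteria are timing, known pattern, no other reasonable explanation, and improvement on de-challenge.
- **Definite (5.11.5)**: all four of timing, no other explanation, known pattern, and a third criterion that accepts immediate onset, de-challenge or re-challenge. A note to that third criterion adds that "a category of definitely related can only be used when recurrence is observed".

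Section 6.1.4 lists, under other safety data, "Adverse events along with their severity and potential relationship to study treatment". No section ranks the categories, gives a default, or says how to score a criterion that could not be assessed because the drug was never stopped or never restarted.

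**The concern.** A count-based scale gives one answer per event only if the counts cannot be met together and always cover the case. Here another possible cause counts towards both Unlikely and Possible. Timing plus known pattern already satisfies Possible and also supplies two of the three criteria that Probable needs. Some events reach no minimum at all.

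What is at stake is the consistency of one planned safety output. Safety is the primary endpoint, the groups have 5 or 10 patients, and the analysis is descriptive, so readers will look at small counts. If one patient's only related event changes category, a group's related-event proportion moves by 1/5 = 20 or 1/10 = 10 percentage points. The formal statistical plan promised in 6.1 can regroup categories later, but it cannot restore consistency to ratings already made at the sites.

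**Working it through.** The plan states no figure to reproduce. The check is an enumeration of the rules.

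**Inputs (5.11.2 to 5.11.5).** T = reasonable timing; K = known pattern; O = another cause could explain the event; D = improved on de-challenge (D− covers both not improved and never taken off); R = re-challenge result. Each of T, K, O, D is 1 or 0.

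**Rules.**
- Unlikely: (1−T) + O + (1−K) + [R negative] ≥ 2
- Possible: T + K + O ≥ 2
- Probable: T + K + (1−O) + D ≥ 3
- Definite: T, K and not O, plus the third criterion, with the recurrence note applied (R positive)

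**Reading choices.** The word *immunization* is read as study drug administration. A re-challenge not done is scored as criterion not met. Possible causes and readily available causes are both coded as O. Not Related is left out because it has no count.

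**Results.** U = Unlikely, Po = Possible, Pr = Probable.

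| T K O | Not re-challenged, D+ | Not re-challenged, D− | Negative re-challenge, D+ | Negative re-challenge, D− |
|---|---|---|---|---|
| 1 1 1 | Po, Pr | Po | U, Po, Pr | U, Po |
| 1 1 0 | Po, Pr | Po, Pr | Po, Pr | Po, Pr |
| 1 0 1 | U, Po | U, Po | U, Po | U, Po |
| 1 0 0 | Pr | none | U, Pr | U |
| 0 1 1 | U, Po | U, Po | U, Po | U, Po |
| 0 1 0 | Pr | none | U, Pr | U |
| 0 0 1 | U | U | U | U |
| 0 0 0 | U | U | U | U |

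- **Not re-challenged:** 7 of 16 meet two minimums (4 Unlikely with Possible, 3 Possible with Probable), 7 meet one, 2 meet none.
- **Negative re-challenge:** 10 of 16 meet more than one, 6 meet one, 0 meet none. Eight of the 10 pair Unlikely with Possible or Probable.
- **Positive re-challenge:** 7 of 16 meet more than one, 2 meet none. Over all three states this is 7 + 10 + 7 = 24 of 48 and 2 + 0 + 2 = 4 of 48.

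**Sensitivity.**
- Timing met only (first four rows), not re-challenged: 5 of 8 meet two, 1 meets none.
- Probable read as exactly three: row 1 1 0 with D+ scores 1 + 1 + 1 + 1 = 4 and drops out of Probable, so 7 becomes 6 and 10 becomes 9.
- A re-challenge not done scored as criterion met: the negative re-challenge columns apply, 10 of 16 and 0.

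**Definite.** A well-timed, known-pattern, otherwise unexplained event with immediate onset meets all four listed criteria, yet the note excludes it unless it recurs.

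**The case against.** The strongest reply is that each heading states a minimum, which is a necessary condition. The criteria lists are introduced permissively, and the lead-in sentences ask for medical judgement that could separate the categories. An event that reaches two minimums is then not placed in both; the investigator chooses. That stands as far as it goes. It does not remove the point, because the lead-ins do not separate neighbours cleanly. Possible is described as a connection that looks unlikely but is not excludable, and Unlikely as an event judged unrelated, which shades into Not Related. Judgement also does not help an event that reaches no minimum.

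Several stronger readings are tempting, and the documents do not support them.

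- **A new, well-timed, unexplained event has no category.** This is true only if it has not improved off drug, or was not taken off, and there is no negative re-challenge. If it improves on de-challenge it meets Probable. If it does not recur on re-administration it meets the minimum for Unlikely.
- **Absence of re-challenge can be taken as the normal case.** Section 5.14 pauses dosing for grade 1 or 2 events and allows it to continue. Section 5.13 treats the grade 2 pause as discretionary; those two sections need reconciling in their own right. Either way, re-exposure is foreseeable.
- **Probable without timing is a material loophole.** The footnote in 5.11.2 ties timing to the drug having been present before the event, so improvement on withdrawing a drug that was not present beforehand is close to an empty cell. The same doubt touches the other untimed profiles, including one of the two that meet no category.
- **The timing phrase in Possible makes the category unusable.** The lead-in to Possible and the other categories refer to the study drug. The phrase is carried-over text and an editorial error.

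**Conclusion.** The point holds as a defect in how causality is coded. The criteria overlap, leave gaps, and have no precedence or default rule, and Definite contradicts its own note. Two raters who follow the text can differ, including across Unlikely and Possible.

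The size is 7 of 16 profiles with two minimums and 2 with none when the drug is not given again, and 10 of 16 with more than one and 0 with none after a negative re-challenge. These counts rest on the reading choices stated above and are logical combinations. A reader might take them as the share of events that will be misclassified; the documents give no event frequencies that would allow that.

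A reader might also infer that the primary safety endpoint itself is not reproducible. The endpoint and objective are defined by adverse events, examination, laboratory measures, vital signs and EKG, and none of those definitions mentions relatedness. Relationship is one descriptive output under other safety data in 6.1.4, and the rules in 5.13 and 5.14 work by grade. Event incidence, severity and the other safety measures are unaffected. Correction is worthwhile because it is cheap and because the ratings cannot be repaired at the analysis stage.

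**What to change.** In 5.11:

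- State one precedence rule. For example: assign the highest category met, except that a negative re-challenge bars Probable and Definite. Without that exception, an event with timing, known pattern, another cause, improvement off drug and no recurrence would be rated Probable, overriding the only criterion that uses a negative re-challenge.
- State one conservative default for events that meet no category, for example Possible.
- Make the third criterion of Definite and its note agree.
- Replace *immunization* in 5.11.3 with study drug administration. This repairs the timing phrase only; the overlaps and gaps counted above already assume it.

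In 6.1.4, state which categories count as related.

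Applied to the 48 profiles, the example rules give exactly one of the four count-based categories each time. The choice of precedence and default is partly a matter of preference; what matters is that one of each is fixed before sites rate events.

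The cost is a few sentences and site training, and a few more events may be counted as related.
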